## **6 STUDY ASSESSMENTS**

### **6.1 SAFETY ASSESSMENTS**

This study has been risk assessed by the Medical Physics and Infection Control teams at the Royal Infirmary of Edinburgh. An Infection Control agreed SOP for cleaning the AliveCor Heart Monitor Device prior to re-use is included in the study paperwork.

### **6.2 STUDY ASSESSMENTS**

Potentially eligible ED and AMU participants will be identified and assessed for study inclusion by the attending clinician. Written consent will be taken and participants will have a Case Report Form (CRF) completed and a 12-lead ECG taken if not already performed by the clinical team.

All STUDY arm participants will be given an AliveCor Heart Monitor and trained in the use of the device and app in the ED or AMU by the research team.

CONTROL arm participants will receive no other intervention.

Participants in both groups will be admitted, referred or discharged by the treating clinician according to current local hospital protocols.

Participants in both groups will be followed up at 90 days through hospital record systems (paper or electronic depending on local policy), GP records and by telephone by the local study team. Participants will also be asked to complete a standardised written questionnaire and will receive a follow-up telephone call from the local study team enquiring about symptoms and contact with medical services. Participants will also be asked about satisfaction and compliance with the heart monitor.

Participants allocated to the Study arm may be contacted by telephone by the local research team shortly after randomisation in the event of them requiring further training or setting up of the device. For example, this may be necessary if a participant does not have their app store password with them in the ED or AMU. If a local electronic patient record system is available, then a research alert will be placed on this stating that the participant has consented to be part of the IPED study.

If a participant allocated to the Study arm, gets an episode of palpitations or pre-syncope and is able to record an AliveCor Heart Monitor ECG during the episode, the participant will email the ECG recorded by the AliveCor app directly to the co-ordinating Edinburgh research team at a convenient time to the participant and to a secure nhs.net email address. This email includes a pdf attachment of the ECG tracing along with the participant's AliveCor app login (which will be their IPED study number - no identifiable participant data will leave the local site, only the participants email address and IPED study number will appear), time and date of recording, and ECG recording. AliveCor collects non-sensitive usage data through a third party service called Mixpanel. Participant will not be asked to send their ECGs to AliveCor directly for analysis. The AliveCor app rhythm analysis algorithm will automatically report any ECG recorded by the AliveCor app as Normal, Atrial Fibrillation or Unclassified.

The co-ordinating Edinburgh research team will review the ECG and will contact the local study team to arrange follow-up if required. If specialist follow-up of the ECG tracing is not required then the local study team will write to the participant informing them of this (Patient ECG follow-up letter normal v2.0 24082016 and Patient ECG follow-up letter abnormal v2.0 24082016) and asking them to arrange follow up with their general practitioner who will be contacted with the report (GP Follow up Letter v2.0 24082016). The participant and GP will not be contacted further should participants record other similar ECGs that similarly do not require specialist follow-up.

If the participant records a serious significant arrhythmia i.e.

- ventricular fibrillation (VF)
- ventricular tachycardia (VT) (it will be assumed that this is symptomatic given the participant has chosen to record an ECG during the episode)
- complete or 3rd degree heart block
- second degree heart block type II (it will be assumed that this is symptomatic given the participant has chosen to record an ECG during the episode)
- pause >6 seconds
- symptomatic bradycardia <40 beats per minute

during the study period, the local study team will alert the participant immediately by telephone, and refer them urgently to their local Emergency Department or cardiac electrophysiology service (as per local protocol).

Participants will be asked to log any symptoms along with the time and date, type of symptom and whether they were able to record an ECG during the symptoms, in a participant symptom diary. They will return this diary to the local research team along with the Participant satisfaction and compliance questionnaire, and smart phone based event recorder at the end of the 90 days in a pre-paid stamped, addressed envelope. Participants will be phoned at 90 days by the local study team to remind them to complete the Participant satisfaction and compliance questionnaire and to return this to the local study team with the symptom diary and smart phone based event recorder. The compliance questionnaire is designed to capture whether participants had the device with them and were able to record a heart tracing during symptoms. This will be entered onto the study database by the local study team.

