## **SUMMARY**

Palpitations (noticeable pounding, fluttering or irregular heart beat) and pre-syncope (near blackout) are common ED problems sometimes due to an abnormal cardiac rhythm. This is difficult to diagnose as examination and electrocardiogram (ECG) are commonly normal and symptoms have usually resolved by the time the patient arrives in the ED. Diagnosing an abnormal heart rhythm as the cause of symptoms rests on capturing it on an ECG and patients are usually discharged with advice to return to the ED again for a 12-lead ECG should symptoms recur. We believe a smart phone based event recorder will allow better and earlier diagnosis in patients with a compatible smart phone or tablet, and revolutionise ED care in this area.

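### Participants may email traces at their convenience, so the plan's urgent pathway for six serious rhythms has no time limit on its first step

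*Protocol*

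**What the plan says.** Protocol 6.2 describes what happens when a study-arm participant captures a trace during palpitations or pre-syncope. The participant emails it "directly to the co-ordinating Edinburgh research team at a convenient time to the participant". SAP 4.2.2 has the same instruction. Neither document gives a latest time for sending.

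The app's algorithm "will automatically report any ECG recorded by the AliveCor app as Normal, Atrial Fibrillation or Unclassified". The manufacturer provides no separate reading: "Participant will not be asked to send their ECGs to AliveCor directly for analysis". Interpretation falls to the co-ordinating team, which "will review the ECG and will contact the local study team to arrange follow-up if required".

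Protocol 6.2 then lists six serious rhythms. If one is recorded, "the local study team will alert the participant immediately by telephone, and refer them urgently" to the local ED or electrophysiology service. SAP 4.2.2 keeps this duty without listing the rhythms.

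Two telephone contacts with study-arm participants are described apart from calls about a trace. Soon after entry they "may be contacted by telephone by the local research team shortly after randomisation" if they need help with training or set-up. At the end, "Participants will be phoned at 90 days by the local study team to remind them" about the questionnaire, and about returning it with the diary and the device.

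**The concern.** The sponsor judged six rhythms serious enough to need an immediate call and urgent referral. The trigger for that call is an email whose timing is left to the participant. This is a stated instruction, so the point does not rest on silence in the text. A participant who follows it exactly may hold a trace of ventricular tachycardia or a long pause until it suits them to send it. However promptly both teams then act, they cannot recover that time.

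The participant sees one of three labels on the phone, and none corresponds to a rhythm on the urgent list. The label therefore cannot identify the trace that should be sent without delay. What is at stake is participant safety. The point has no bearing on the primary comparison.

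**Working it through.** No figure in the plan needs reproducing. The check sets the steps of the pathway side by side, compares two lists, and looks for any other prompt to send.

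**1. Steps from recording to alert (Protocol 6.2)**

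| Step | Who acts | Timing stated |
|---|---|---|
| Record the trace | Participant | During the episode |
| Email the trace | Participant | At the participant's convenience |
| Review the trace | Co-ordinating team | None |
| Contact the local team | Co-ordinating team | None |
| Telephone and refer | Local team | Immediately, urgently |

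Each step depends on the one before it. The email shows only an email address and a study number, so the telephone call has to go through the local team. The time from recording to alert is the sum of the delays at sending, review, hand-over and calling. Only the last has a speed requirement, and sending is the only one whose timing is expressly left open.

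**2. App labels against the urgent list**

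- Labels: normal, atrial fibrillation, unclassified. Count = 3.
- Urgent rhythms: ventricular fibrillation; ventricular tachycardia; complete heart block; type II second degree block; a pause over 6 seconds; symptomatic bradycardia below 40 per minute. Count = 6.
- Urgent rhythms named by a label: 0 of 6.

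Protocol 1.1 notes that someone who has lost consciousness cannot trigger an event recorder, so ventricular fibrillation is an unlikely capture. Leaving it out gives 0 of 5, and the conclusion is the same. The unclassified label could cover an urgent trace, but nothing in the text marks it as urgent. The documents do not say which label the app would give each rhythm, and none is assumed here.

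**3. Other prompts to send a trace**

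- The early call is optional and concerns training and set-up.
- The day-90 call concerns the questionnaire, diary and device. It is not described as a check for unsent traces.
- The symptom diary records whether a trace was obtained, but it is returned only at the end of follow-up.
- Protocol 6.1 mentions Medical Physics and Infection Control assessments and a cleaning procedure. It does not mention the timing of traces.

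None of these prompts a participant to send a trace sooner.

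**The case against.** The strongest reply is that trace review is added on top of standard care, which the study arm keeps (Protocol 5.5.2). The Summary and section 1.1 describe the usual advice to return to the ED or phone 999 if symptoms recur. A trace is recorded during symptoms, so the event that produces it is also the event that triggers that advice. This stands, and it limits the risk considerably. The documents do not show that a late sender is worse off than under standard care alone. The advice is, however, described as usual practice and is not restated as an instruction to study-arm participants.

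It can also be said that the plan never asks participants to triage by label, and that the duty to act immediately binds the local team only once a trace has been reviewed. Both are fair. There is no contradiction in the text, and false reassurance from a label is not shown. What remains is that the time before review is unlimited.

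Finally, the information sheet and device training may already tell participants to send promptly and to seek help. That is possible, and their absence from the documents reviewed is not evidence against it. The protocol and SAP wording would still need to agree with them.

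Two stronger readings are tempting and should be resisted. A reader might infer a delay of up to 90 days because the next fixed call is at day 90. That call is not about unsent traces, so it does not set a bound. A reader might also infer, from the Summary's remark that "symptoms have usually resolved by the time the patient arrives in the ED", that participants who recover will not seek care. The remark describes people who did attend after recovering, so it does not support that inference.

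**Conclusion.** The point holds as a modest safety improvement. The plan's own urgent pathway has no time limit on its first step, no app label names any of the six rhythms, and no stated step prompts earlier sending.

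Its size in practice is unknown. The documents give no sending times, no rate for the listed rhythms and no expected delay, so no number of affected participants is claimed. Protocol 1.1 says serious arrhythmia is less likely in these patients than in those with syncope. The conclusion rests on the protocol and SAP text alone and would weaken if the participant materials already give prompt-sending and emergency instructions. How often the mailbox is read and who deputises for the local contact are not stated either. Those are operational details, and the point does not depend on them.

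**What to change.** In Protocol 6.2, and in SAP 4.2.2 for consistency, replace the phrase about the participant's convenience with: as soon as they are able, and on the same day.

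Add to Protocol 6.2 that participants are told at device training that:

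- the app label does not identify these serious rhythms;
- the study mailbox is not an emergency service;
- the advice to return to the ED or phone 999 applies whatever the label shows.

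The list of rhythms and the immediate telephone alert stay as they are. A stated mailbox-reading frequency and a deputy contact at each site would be optional additions; they are operating commitments and go beyond a change of wording.

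The cost is slightly more burden on participants and a submission to the REC and local R&D under Protocol 13.1. The analysis does not change. Some participants will still send late. If the participant materials already say this, only the protocol and SAP wording needs aligning.

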## **7 DATA COLLECTION**

Participants will have a CRF completed during index hospitalisation, comprising demographic, historical and examination characteristics. An ECG will also be taken and stored. Participant contact details will also be confirmed including a telephone number and email address. Once a participant has been randomised, the baseline CRF will be sent to the local study team office. The information on the CRF will be entered into a specially designed password protected online accessed secure database (REDCAP; <http://www.project-redcap.org>) the server of which is held within the University of Edinburgh. No participant identifiable information will leave the recruiting NHS hospital or be entered onto REDCAP. Participants will be identified on REDCAP by study number alone.

## **8 STATISTICS AND DATA ANALYSIS**

### **8.1 SAMPLE SIZE CALCULATION**

Using a symptomatic rhythm detection rate at 90 days of 25% [3] versus standard care (10%) we estimate 110 participants in each group would have 80% power to determine a 15% improvement in symptomatic rhythm detection. We will recruit an extra 10% in each arm to allow for drop out (i.e. 121 participants in each arm). Our ED sees around 500 eligible participants a year. Assuming a 50% recruitment rate we estimate we will need to recruit for 15 months.

### **8.2 PROPOSED ANALYSES**

Descriptive analysis of participant characteristics shall be presented split by study arm. Baseline to 90 day change in diagnostic yield between the two study arms will be analysed using two sample t-tests or non-parametric equivalent as appropriate. Log-rank tests and Kaplan-Meier curves shall be used to examine if the smartphone recorder has an effect on detecting symptomatic rhythm and cardiac arrhythmia separately up to 90 days versus standard care. Categorical variables will be compared using a  $\chi^2$  test (and  $\chi^2$  test for trend if appropriate). All participants will be analysed on an intention to treat basis.

## **9 ADVERSE EVENTS**

A secondary endpoint for the study is serious outcomes at 90 days: all cause death and major adverse cardiac events [MACE] (myocardial infarction, life-threatening arrhythmia, insertion of a pacemaker or internal cardiac defibrillator, insertion of pacing wire). This data will therefore be routinely collected as part of the study and not recorded as an Adverse Event (AE). Hospital admission will also not be recorded as an AE. The only AEs recorded will be those directly related to the use of the smart phone based event recorder and application.

## **10 PREGNANCY**

Pregnancy is not an exclusion criteria for the IPED study.

## **11 TRIAL MANAGEMENT AND OVERSIGHT ARRANGEMENTS**

### **11.1 TRIAL MANAGEMENT GROUP**

The study will be coordinated by a Project Management Group consisting of the Chief Investigator, Co-Investigators, Statistician and Research Team.

EMERGE will oversee the study and will be accountable to the Chief Investigator. EMERGE will be responsible for checking the electronic CRFs for completeness, plausibility and consistency. The Chief Investigator and EMERGE will resolve any queries.

A Delegation Log will be prepared detailing the responsibilities of each member of staff working on the study.

### **11.2 TRIAL STEERING COMMITTEE**

A Trial Steering Committee (TSC) has not been convened for this study. An independent advisor has been appointed to oversee the conduct and progress of the study.

### **11.3 DATA MONITORING COMMITTEE**

An independent Data Monitoring Committee (DMC) has not been convened for this study.

### **11.4 INSPECTION OF RECORDS**

Investigators and institutions involved in the study will permit study related monitoring and audits on behalf of the sponsor, Research Ethics Committee (REC) review, and regulatory inspection(s). In the event of an audit or monitoring process being implemented, the Investigators agree to allow the representatives of the sponsor direct access to all study records and source documentation. In the event of regulatory inspection, the CI agrees to allow inspectors direct access to all study records and source documentation.

### **11.5 RISK ASSESSMENT**

An independent risk assessment may be performed by an Academic and Clinical Central Office for Research and Development (ACCORD) Clinical Trials Monitor to determine if monitoring is required and if so, at what level although this is unlikely as the study is not a CTIMP or high risk study. An independent risk assessment may also be carried out by the ACCORD Quality Assurance Group to determine if an audit should be performed before/during/after the study and if so, at what locations and at what frequency.

### **11.6 STUDY MONITORING AND AUDIT**

An ACCORD Clinical Trials Monitor or an appointed monitor may visit the Investigator's site prior to the start of the study and during the course of the study if required, in accordance with the monitoring plan if required. Risk assessment will determine if audit, by the ACCORD QA group, is required. Details will be captured in an audit plan. Audit of the Investigator's site,

study management activities and study collaborative units, facilities and 3rd parties may be performed.

## **12 GOOD CLINICAL PRACTICE**

### **12.1 ETHICAL CONDUCT**

The study will be conducted in accordance with the principles of the International Conference on Harmonisation Guideline for Good Clinical Practice (ICH GCP) and the Research Governance Framework for Health and Community Care (Scotland) 2006 [9].

A favorable ethical opinion will be obtained from the appropriate REC and local Research and development (R&D) approval will be obtained prior to commencement of the study.

### **12.2 INVESTIGATOR RESPONSIBILITIES**

The Principal Investigator is responsible for the overall conduct of the study at the site and compliance with the protocol and any protocol amendments. In accordance with the principles of ICH GCP, the following areas listed in this section are also the responsibility of the Investigator. Responsibilities may be delegated to an appropriate member of study site staff.

#### **12.2.1 Informed Consent**

The Principal Investigator is responsible for ensuring informed consent is obtained before any protocol specific procedures are carried out. The decision of a participant to participate in clinical research is voluntary and should be based on a clear understanding of what is involved.

Participants must receive adequate oral and written information – appropriate Participant Information and Informed Consent Forms will be provided. The oral explanation to the participant will be performed by the Principal Investigator or qualified delegated person, and must cover all the elements specified in the Participant Information Sheet and Consent Form.

The participant must be given every opportunity to clarify any points they do not understand and, if necessary, ask for more information. The participant must be given sufficient time to consider the information provided. It should be emphasised that the participant may withdraw their consent to participate at any time without loss of benefits to which they otherwise would be entitled.

The participant will be informed and agree to their medical records being inspected by regulatory authorities and representatives of the sponsor(s) but understand that their name will not be disclosed outside the hospital.

The Principal Investigator or delegated member of the study team and the participant will sign and date the Informed Consent Form to confirm that consent has been obtained. The participant will receive a copy of this document and a copy filed in the Investigator Site File (ISF) and participant's medical notes.

#### **12.2.2 Study Site Staff**

The Principal Investigator must be familiar with the protocol and the study requirements. It is the Principal Investigator's responsibility to ensure that all staff assisting with the study are adequately informed about the protocol and their study related duties.

#### **12.2.3 Data Recording**

The Principal Investigator is responsible for the quality of the data recorded in the CRF at the Investigator Site.

#### **12.2.4 GCP Training**

The Chief Investigator, Principal Investigators and Lead Research Nurse Co-ordinator should hold evidence of GCP training and ensure staff are aware of the guidelines. All staff on the delegation log should have appropriate and relevant training in the research tasks that they undertake.

### **12.2.5 Confidentiality**

All evaluation forms, reports, and other records must be identified in a manner designed to maintain participant confidentiality. All records must be kept in a secure storage area with limited access. Clinical information will not be released without the written permission of the participant. The Principal Investigators and study site staff involved with this study may not disclose or use for any purpose other than performance of the study, any data, record, or other unpublished, confidential information disclosed to those individuals for the purpose of the study. Prior written agreement from the sponsor or its designee must be obtained for the disclosure of any said confidential information to other parties.

### **12.2.6 Data Protection**

Data will be initially collected into a paper CRF and then entered into a specially designed password protected online accessed secure database (REDCAP; <http://www.project-redcap.org>) the server of which is held within the University of Edinburgh. No participant identifiable information will leave the NHS or be entered onto REDCAP. Participants will be identified on REDCAP by study number alone.

Identifiable electronic information will be kept in a separate database, which will not be accessible outside the immediate research team. This data will be linked by study number to the anonymised research database and will be stored on a secure, password protected location on the local hospital computer drive and only accessible to relevant staff.

Identifiable non-electronic data of the participant will be kept in a locked filing cabinet in a locked local research study office.

Data entry will be completed by the local research team and data analysis by the study statistician. No participant identifiable data will be transferred outwith the local NHS region. Participant identifiable data will be removed from electronic data being sent to the University of Edinburgh for analysis.

The Chief Investigator will be responsible for the quality of the data recorded in the electronic CRF on the research database.

All Investigators and study site staff involved with this study must comply with the requirements of the Data Protection Act 1998 with regard to the collection, storage, processing and disclosure of personal information and will uphold the Act's core principles. Access to collated participant data will be restricted to those clinicians treating the participants, representatives of the sponsor and representatives of regulatory authorities.

Computers used to collate the data will have limited access measures via user names and passwords.

Published results will not contain any personal data that could allow identification of individual participants.

